Specific Aim 2: Pilot test the 7-week BullyDown primary prevention program for feasibility and acceptability in an RCT of 150 middle adolescents. Youth will be randomly assigned to either BullyDown, a 4-message-per-day program, or an attention-matched control group talking about ‘healthy lifestyle’ topics (e.g., exercise). Our main outcome measures will be feasibility (e.g., recruitment and enrollment rates) and acceptability (e.g., positive program appraisal) at intervention end. The behavioral outcomes we will measure to motivate power analyses for a future R01 include: (1) bullying perpetration, (2) other aggressive behavior directed towards peers, and (3) bystander behavior in the past 30 days at 3-month post-intervention. We also will examine behavioral indicators at intervention end to observe proximal effects.

Given the limited impact of existing school-based interventions and the time associated with implementing them during school time, more efficient and effective intervention methods are needed. Programs that can be delivered to youth in middle adolescence, typically of middle school aged, irrespective of whether they are attending school physically or virtually may be especially relevant as school boundaries become more fluid. BullyDown addresses this critical need by providing a scalable program that could be quickly and cost-effectively disseminated nationally. If efficacious, we will test the intervention in an R01-funded RCT. Future endeavors could include adapting the program for Spanish-speaking youth and dynamically tailoring content to reported bullying behaviors.

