3. RESEARCH PROTOCOL

3A. DESCRIPTION OF STUDY POPULATION, INCLUSION AND EXCLUSION CRITERIA

Study Sites. [name] has a strong relationship with the Chatham County School District (See Letter of Support). There are 8 middle schools in the District, with a combined enrollment of 712 7th graders. The schools are diverse in terms of race and income: 47% are racial/ethnic minority (e.g., 31.5% are Black) and 69% are receiving free or reduced cost lunch. We will randomly select three schools. Should a school choose to opt out, we will randomly select another from the remaining five schools. Note that, while enthusiasm for the program is high, it is against district policy to allow principals to provide Letters of Support.

Should additional sites be needed, we will draw upon local Boys & Girls Clubs. The Boys & Girls Club of America (BGCA) includes over 4,000 clubs in the U.S. and serves approximately 4 million young people. Local clubs affiliated with the BGCA provide young people with a safe, supervised, and constructive environment during non-school hours. The organization serves a diverse population of young people with a large representation from low-income backgrounds. The Boys & Girls Clubs of Durham and Orange Counties serve students in the cities of Durham and Chapel Hill. The clubs are diverse in terms of race and income: 85% are African American, 6% Hispanic, 3% are White, 3% are Asian, 2% are Multiracial, and 1% are American Indian/Alaskan Native. About 62% of students are experiencing financial hardship, 1% have disabilities, and 4% are English Language Learners.

We also may recruit 13-14 year olds using advertisements on social media, such as Facebook and Instagram.

Youth eligibility criteria. The inclusion criteria for youth matches the anticipated profile of users when the program is publicly available in the future. Participants will: be enrolled in one of our partner schools, be in middle school (i.e., 7th or 8th grade) or between the ages of 12-14 years of age, be English-speaking, own their own cell phone, intend to have the same cell phone number for at least 3 months (this may or may not apply, depending on the number of youth who meet this criterion), provide informed written assent, and have parental permission. Non-English speakers and youth who do not have the reading ability to complete the screener are not eligible.

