Youth recruited via social media additionally must be 13 years of age or older due to the Children’s Online Privacy Protection Act.

Justification for eligibility criteria. Excluding Spanish youth: Only 11% of students in the Chatham County School District are English language learners, suggesting that more than 600 of the 7th graders will be English-speaking.

Requiring cell phone ownership: If we gave youth phones, findings would not be generalizable (e.g., community-based organizations are unlikely to provide cell phones). **National data suggest that low income youth are as likely as higher income youth to have cell phones.**¹³ Our District contact estimates that almost all students have a cell phone. Similarly, [name] recently conducted FGs with low-income middle school students and most had a cell phone. As

such, we are not reifying the digital divide with this criterion.

3B. SAMPLE SIZE

We will include ~60 youth in focus groups, ~70 in content advisory teams, 15-20 youth in a beta test if time allows, and 150 in a randomized controlled trial.

For the focus groups, we will enroll about 60 youth to take part in the online discussion. The groups will be stratified by characteristics that we posit will contribute to a sense of shared experiences and/or affect the likelihood of being a perpetrator of bullying. This may include sex, race/ethnicity, among others. We will endeavor to purposefully sample youth so that at least 50% are racial/ethnic minority, at least 50% are receiving free or reduced cost lunch, at least 30% report bullying perpetration and 30% report bullying victimization (note that there may be overlap such that a youth is both a bully and a victim). Actual distributions of youth who screen eligible may result in different ratios. We anticipate partnering with about 7 schools and about 2 BCGA Clubs. We will work with school administrators and Club Directors to determine the optimal school participation for each research activity.

3C. DESIGN AND DESCRIPTION OF METHODOLOGY

Recruitment and enrollment protocol

In person recruitment.

Recruitment and enrollment will be similar for each of the three research activities. Chatham County Public School administration has agreed to dedicate classroom time for us to recruit youth from middle schools. We also will recruit from local Boys & Girls Clubs and via social media.

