First, research staff will visit classes or Clubs to briefly describe the study activity and encourage youth who are interested to complete the screener. If youth are still being taught at home, as they are now in July 2020, the screener will be a brief online survey. If youth are back at their brick and mortar school or Club, the screener will be either online or paper and pencil. The screener will disguise the qualifying criteria so that those interested in participating will not know the “right” answers. [name] team has found this to be particularly important in technology-based interventions where students are especially keen to take part in the study.

Next, youth who are eligible will be invited to an enrollment meeting where the study activity will be discussed, any questions will be answered, and an enrollment packet will be distributed. Research staff will present the study in small groups during times that do not interfere with academic commitments (e.g., during break, lunch). The packet will include the parental permission and youth assent forms; it may also include a cover letter from the school principal or the Club Director as well, depending on the District supervisor’s choice.

Based upon previous experience, we anticipate more youth will be eligible than is our target recruitment number for the pilot RCT (~50 youth per school). As such, youth will be randomly selected to participate among those who are eligible. A list of candidates will be generated by the study software program and students will be contacted sequentially.

Youth who are interested in taking part in the study will receive an enrollment packet that includes both youth assent and parental permission forms. If youth are distance learning, these forms will be available online. If they are back in their brick and mortar setting, the forms will be printed. Research staff will ask youth to bring back their signed parental form and their signed youth assent form within two weeks. We may also have an online version.

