Transcripts of the FGs will be entered into Dedoose (formerly EthnoNotes),⁸⁵ a mixed methods analysis program. Codes will be generated based on the first FG, reexamined, and refined through constant comparison with the second FG.⁸⁶ A codebook will be created with codes, brief descriptions, and illustrative quotations.⁸⁷ Codes will be both generated inductively and derived from our initial research questions (e.g., how youth interact with their peers and their teacher online). [name] project coordinator and [name] graduate research assistant will code both FGs. To assure inter-coder reliability, we will calculate a kappa value and accept a minimum of 0.75 as the criterion for adequate agreement between coders.⁸⁸ After coding is complete, we will extract themes using an iterative process to highlight evidence contradictory to our conclusions as well as the modal response.⁸⁹ The analysis will result in a report that describes the findings and advises how to integrate them into program content.

Specific Aim 2: Pilot test the 7-week BullyDown intervention for feasibility and acceptability in an RCT of 150 adolescents either in middle school and/or 12-14 years of age.

The **feasibility** of the BullyDown intervention will be determined by our recruitment and retention rates. If at least 75% of eligible studies assent and 80% complete the survey at 3-months post-intervention, we will deem these data points as supportive of a hypothesis of feasibility.

The **acceptability** of program features (e.g., badges, Text Buddy) will be measured using 5-point Likert scales; average scores of 4 or more will be supportive of acceptability.⁹⁰ Youth engagement with the program will be examined to identify potential trends in greater intervention impact (e.g., for those who use the Text Buddy feature).

Post-intervention one-on-one interviews to illuminate the intervention experience will be analyzed using a thematic approach,⁹¹ as our aim will be more descriptive in nature, with a lower level of interpretation needed than is afforded by grounded theory or other qualitative analytical techniques.⁹²

Analyses examining **behavioral outcomes** will be primarily intended to inform power analyses for the larger R01. Data will be treated as intention-to-treat and complete case. We will conduct sensitivity analyses (e.g., missing = bullying behavior) to understand how this may affect our findings. Missing data that are not the main outcomes will be imputed.

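### Does the 75% assent criterion for feasibility need a different base or numerator?

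*Combined protocol and SAP*

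**What the plan says.** Section 2 (Specific Aim 2) makes feasibility a main outcome: "Our main outcome measures will be feasibility (e.g., recruitment and enrollment rates" are its examples. Section 3E then ties feasibility to recruitment and retention, with the thresholds "If at least 75% of eligible studies assent and 80% complete the survey at 3-months post-intervention". Meeting them is described only as supporting a hypothesis of feasibility. No section makes progression depend on them.

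Section 3C (In person recruitment) says that "youth who are eligible will be invited to an enrollment meeting where the study activity will be discussed". It also says that "we anticipate more youth will be eligible than is our target recruitment number for the pilot RCT (~50 youth per school"), so candidates are drawn at random from the eligible and contacted one after another. Youth who cannot be contacted, or who decline by their own or a parent's choice, give way to the next on the list. Section 3C (Enrollment) does not count a youth as enrolled until the baseline survey is finished.

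Section 3A lists among the participant criteria that youth "provide informed written assent, and have parental permission". Table 3 in Section 3D monitors eligible and ineligible youth, permission forms received, invited youth who decline, and retention.

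**The concern.** Two things look loose. First, the base. With more eligible youth than places, some eligible youth may never be approached. If they count in the denominator, the rate depends on the size of the pool as well as on willingness. Read literally, the Section 3A list would even make assent part of eligibility, so that the rate is 100% by construction. The criterion is also silent on youth who are approached but never reached.

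Second, the numerator. Section 2 speaks of enrollment, but the threshold is on assent. Active-permission routes also need a parent's agreement, and every route needs a completed baseline survey. Table 3 counts forms received, and the incentive in Section 3C is paid whether or not permission was granted, so that count alone does not give permissions granted.

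This is the only recruitment threshold for a main outcome. At stake is whether the same recruitment data could be called a pass or a fail depending on a choice made after they are seen.

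**Working it through.** The plan gives no derivation for 75%, so there is nothing to reproduce. The targets are consistent: 76 + 74 = 150, and 3 schools × about 50 = 150.

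**Inputs from the documents.** Section 3A: "There are 8 middle schools in the District, with a combined enrollment of 712 7th graders", with three schools to be selected. Section 3A, justification: "Only 11% of students in the Chatham County School District are English language learners". RCT target: 150.

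**Assumed, because not given.** E = number screened eligible; a = assent share of those approached; p = share of assenters with permission granted; recruitment stops at 150.

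**1. All-eligible base.** The number approached is the smaller of E and 150/(a × p). The rate is then the smaller of a and 150/(p × E). Reaching 75% needs a ≥ 0.75 and E ≤ 150/(0.75 × p).
- p = 1: E ≤ 200.
- p = 0.85: E ≤ 235.
- p = 0.85 and an assumed 90% baseline completion: E ≤ 150/(0.75 × 0.85 × 0.90) = 261.

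**2. How large could E be?** English-speaking 7th graders per average school: 712/8 × 0.89 = 79.2.

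| Schools | English-speaking 7th graders | Share eligible to reach 200 (p = 1) | Share to reach 235 (p = 0.85) |
|---|---|---|---|
| 3 | 238 | 84% | 99% |
| 5 | 396 | 50% | 59% |
| 7 | 554 | 36% | 42% |

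Three schools is the stated RCT selection. There, passing 200 is unlikely, because only interested youth complete the screener and they must own a phone. The limit of 261 exceeds all 238. The larger site count in Section 3B, "We anticipate partnering with about 7 schools and about 2 BCGA Clubs", covers all research activities and does not say how many serve the RCT. 8th graders, Clubs or social media would enlarge E by unknown amounts.

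**3. Can the base change the result?** Yes. With 150 assents, 200 approached and 238 eligible: 150/200 = 75%, but 150/238 = 63%. The 63% supposes that every English-speaking 7th grader in three schools is eligible.

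**4. Which base does the text support?** In Section 3C eligible youth are invited, and in Section 4.b they are given forms. In both places eligibility comes before assent, so the 100% reading does not survive. Table 3 counts invited youth who decline; with those who assent, they make up the approached youth who gave an answer.

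**5. Youth not reached.** Suppose 200 are approached, 20 are not reached and 140 assent. The rate is 140/200 = 70% with the 20 in the base and 140/180 = 78% without. Both lie within the 95% Wilson interval for an observed 150/200 (69% to 80%).

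**6. Assent against enrollment.** With a = 0.80 and p = 0.85, 150/0.68 = 221 are approached, 177 assent (80%) and 150 (68%, 95% CI 61% to 74%) could enroll before the baseline step. The p here is parental refusal among youth who returned assent. Section 3C puts both forms in one packet and Section 4.b obtains assent in the same way as permission. A packet that never comes back therefore lowers the assent rate too. For social media, where a waiver is requested, the permission step drops out if it is granted.

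**The case for a change.** The strongest case for a change is that feasibility is what this pilot exists to measure. A denominator settled after the data are in can decide the answer, and one sentence would prevent that. Section 4.b reports that only half of the active forms given to eligible Club youth came back, so permission can be the bottleneck. The not-reached and numerator questions do not depend on pool size.

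Part of this stands. Section 3E does not say how youth approached but not reached are counted, and step 5 shows that this can move a result across 75%. Enrollment is named in Section 2 without a threshold.

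The rest is weaker. The Club figure is a share of forms given out, not of youth who assented; with both forms in one packet, a low return shows up in the assent rate itself. Section 2 offers enrollment as an example and promises no threshold for it. Permission granted must be known to run the trial, because the confirmation text goes out only after both agreements are in hand and parental refusals trigger replacement. The two worries also partly offset each other: at p = 1 the permission gap vanishes, and as p falls the limit on E rises.

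**Conclusion.** No change is needed. The criterion leaves a definition unstated, and analysts would fill it sensibly: youth approached is the base that matches sequential contact and Table 3, and on it the 75% rule is workable. The all-eligible base would defeat the rule only above 200 eligible youth (235 if 85% of assenters have permission), which is unlikely in the stated three-school design but less so if more sites serve the RCT. The gap between assent and enrollment is limited mainly to parental refusals and unfinished baselines. Its illustrated size, 80% against 68%, rests on assumed shares.

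A different base, a sensitivity rate or rates by recruitment route would add reporting without correcting a result shown to be wrong. Route-level rates would also be imprecise: 30/40 is 75% with a 95% CI of 60% to 86%. The 75% threshold would stay where it is, and the rule carries no progression decision. When results are written up, the numbers approached, not reached, assenting, permitted and randomized can be set out in sequence, so that a reader can form any of these rates.

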Data collection. Measures will be collected online at baseline, intervention end, and 3 months post-intervention end. All participants, regardless of study condition, will complete assessments at each time point. Youth will be able to complete the surveys on their own (e.g., at home). If they are attending the brick and mortar school or Club, they also will be able to complete the survey at school or Club in the computer lab if they would prefer. To facilitate self-completion, youth will receive an invitation text message with a unique URL to access the survey. This allows participants to complete the survey at a time and place convenient for them. Alternatively, they can sign up for one of the survey sessions at school or Club that the research staff will schedule with the school or Club administration. To avoid unintentional influence that school and Club staff may have on youth survey answers, only research staff will be present in the computer lab during survey administration.

3D. MEASUREMENTS AND STUDY INSTRUMENTS

Most of the proposed measures below were used in the beta test, suggesting the survey length can be feasibly completed by adolescents in middle school or between the ages of 12-14 year of age. Measures are as follows:

Table 3. BullyDown assessment measures		
Main Outcome measures (intervention end)	Acceptability	We will measure intervention acceptability and tolerability ⁶⁷ with a combination of open-ended questions (e.g., “What aspect of the program did you like the least?”) and questions that form a scale of intervention acceptability (e.g., I liked my Text Buddy; $\alpha = .87$). Participants will estimate the number of messages they received in the past week and percent that they read. The program will record the number of weekly level-up questions answered, and the number answered correctly, as well as the number of Text Buddy and Forever Friend messages sent.
	Feasibility	We will monitor the number of eligible/ineligible youth, the number of parental permission forms received, the number of youth invited but who decline to take part, and the retention rate.

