Preliminary behavioral outcome measures (Intervention end and 3-month follow-up)	Bullying perpetration	Bullying will be queried by type (e.g., relational, physical), mode (e.g., online, in-person), and place (e.g., at home, at school). ⁶⁸ Youth who endorse any question at a frequency of 3 times or more in the past 30 days (to reflect repetitive behavior) will be coded as engaging in bullying.
	Other aggression	Youth who report engaging in the above bullying perpetration items, but less frequently so, will be coded as engaging in aggressive acts. ⁶⁸
	Bystander behavior	Youth will be asked if, in the past 30 days, they have seen or heard about (e.g., as a rumor) someone being bullied. Those who say yes will be asked what they did in response. Options will include: nothing, telling an adult, talking to the victim, and standing up to the bully.

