Baseline covariates will be examined to determine whether randomization performed as intended. Any that are significantly imbalanced across study arms will be included in multivariate analyses.

We will use logistic regression to analyze outcomes (e.g., bullying perpetration, other aggressive behaviors; bystander behavior). Once gross estimates of intervention effect have been calculated, covariates will be added to examine

whether they appear to mediate the relation between group assignment and the outcome. Three conditions must be met in order to claim that mediation is present:⁹³⁻⁹⁵ (1) a predictor (e.g., experimental arm) is significantly associated with a mediator (e.g., TPP motivation); (2) The mediator is significantly associated with an outcome (e.g., pregnancy); and (3) when one controls for the mediator, the effect of the predictor on the outcome becomes non-significant. If this effect retains significant but is attenuated, partial mediation is indicated. A 10% or greater change in the point estimate will be deemed clinically significant.^{96,97}

Sex as a biological variable. It is possible that males will respond to the program differently than females because it feels more individual and perhaps, in this way, will resonate more with males.⁸³ Conversely, perhaps because females text message at a greater volume than males,^{36,84} the format of this program may resonate more with them. As such, sex will be explicitly examined as a potential moderator. To understand whether the intervention impact varies by sex, we will test an interaction term, i.e., experimental group X sex. If the term is statistically significant, then it will suggest that boys and girls are impacted differentially by the intervention.

To examine whether/how the intervention effect attenuates over time, we will use generalized estimation equations to analyze the data across follow-up periods using an identity link and exchangeable correlation structure. By entering an interaction term for experimental group X time, we can determine if the intervention is differently impactful at intervention end versus 3-months post-intervention.

Should [name] need statistical guidance, we will take advantage of [name] access to the biostatistics 'core' at the University of North Carolina (please see Budget Justification).

Power analysis

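### The behavioural analysis is called intention-to-treat but is a complete-case analysis of responders, its imputation sentence does not fit the plan's own outcome labels, and the lead estimate is not adjusted for baseline bullying.

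*Combined protocol and SAP*

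**What the plan says.** Section 3E, in the paragraph on behavioural outcomes, sets three rules in consecutive sentences:

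- The analysis set is described this way: "Data will be treated as intention-to-treat and complete case".
- Missing outcomes get a sensitivity analysis, with one example named: missing = bullying.
- The imputation rule is worded by exclusion: "Missing data that are not the main outcomes will be imputed".

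The term main outcomes is fixed elsewhere. Specific Aim 2 in section 2 says: "Our main outcome measures will be feasibility (e.g., recruitment and enrollment rates) and acceptability (e.g., positive program appraisal) at intervention end". Table 3 in section 3D puts acceptability and feasibility under the label "Main Outcome measures (intervention end". It puts bullying perpetration, other aggression and bystander behaviour under "Preliminary behavioral outcome measures (Intervention end and 3-month follow-up".

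On the model, section 3E says: "We will use logistic regression to analyze outcomes (e.g., bullying perpetration, other aggressive behaviors; bystander behavior". Crude estimates of effect come first. Baseline covariates enter multivariate models if they differ significantly between arms, and other covariates are added later to look at mediation. The behavioural analyses as a whole "will be primarily intended to inform power analyses for the larger R01".

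The plan does not define the intention-to-treat set, give an imputation method or list of variables, or say which analysis leads.

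**The concern.** There are three linked problems.

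First, intention-to-treat normally means that every randomised participant is analysed in the assigned arm. Complete case removes those without the outcome. One label cannot describe both sets, and a reader of the eventual report would not know which was used. Section 3C adds a further ambiguity: youth who miss the intervention-end survey are still surveyed at 3 months, and the plan does not say whether they count as complete cases.

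Second, the imputation sentence is defined by exclusion, and the excluded term has a meaning elsewhere in the plan that does not suit this paragraph.

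Third, the baseline survey is finished before randomisation, so baseline bullying should be available for essentially everyone. It is a plausible predictor of both dropout and later bullying, yet nothing commits the lead model to using it. It may be a minimisation factor (section 3C). If so, it will tend to be balanced at randomisation, and the rule of adjusting only for significant imbalance is unlikely to bring it in.

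At stake is the effect estimate that would be carried into the R01 sample size.

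**Working it through.** The plan gives no power, alpha or effect-size figure for this analysis, so there is none to reproduce. The check has three parts.

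**1. How many youth the label leaves out.** Inputs: 150 randomised (76 and 74, section 3C); an 80% completion threshold at 3 months (section 3E); 88% retention at 12 months in an earlier study cited in section 3C.

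- At 80%: 0.80 × 150 = 120 analysed, 30 left out.
- At 88%: 0.88 × 150 = 132 analysed, 18 left out.

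**2. What the imputation sentence covers.**

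- If main outcomes has the meaning given in Aim 2 and Table 3 (feasibility and acceptability), the behavioural outcomes are not main outcomes and would be imputed. That clashes with complete case two sentences before.
- If it means the behavioural outcomes, the subject of the paragraph, then only covariates and other measures are imputed and the paragraph is consistent. The term then disagrees with Aim 2 and Table 3.

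One wording or the other has to change.

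**3. What an unadjusted complete-case odds ratio can do.** All inputs here are assumptions for illustration. The 22% baseline bullying rate is the midpoint of the 20–24% background figure in section 1. Follow-up bullying is taken as 60% in baseline bullies and 10% in others, the same in both arms, so there is no true effect. The true follow-up rate is 0.22 × 0.60 + 0.78 × 0.10 = 21.0% in each arm.

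If an arm retains a fraction r_b of baseline bullies and r_o of others, its complete-case rate is

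(0.22 × r_b × 0.60 + 0.78 × r_o × 0.10) / (0.22 × r_b + 0.78 × r_o).

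For r_b = 0.60 and r_o = 0.86: 0.14628 / 0.8028 = 18.2%, with overall retention 80.3%. For r_b = r_o = 0.80: 0.168 / 0.80 = 21.0%. The odds ratio is (0.1822/0.8178) / (0.21/0.79) = 0.84.

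| Retention, BullyDown (bullies / others) | Retention, control (bullies / others) | Observed rates | Odds ratio |
|---|---|---|---|
| 60% / 86% | 80% / 80% | 18.2% vs 21.0% | 0.84 |
| 70% / 83% | 80% / 80% | 19.6% vs 21.0% | 0.92 |
| 75% / 81.5% | 80% / 80% | 20.3% vs 21.0% | 0.96 |
| 60% / 86% | 60% / 86% | 18.2% vs 18.2% | 1.00 |
| 80% / 80% | 60% / 86% | 21.0% vs 18.2% | 1.19 |

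In every row, the rates within each baseline group are 60% vs 60% and 10% vs 10%. A complete-case logistic model with arm and baseline bullying therefore gives an arm odds ratio of 1.00.

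The one sensitivity analysis that the plan names does not recover the null in the first row. Missing = bullying gives 0.14628 + 0.1972 = 34.3% against 0.168 + 0.20 = 36.8%, an odds ratio of 0.90.

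For scale, the first row has about 61.0 and 59.2 responders. The standard error of the log odds ratio is √(1/11.12 + 1/49.90 + 1/12.43 + 1/46.77) = 0.46. The log of 0.84 is −0.18, about 0.38 standard errors, with an approximate 95% interval of 0.34 to 2.07.

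**The case against.** Several objections stand in part.

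- **The imputation sentence has a natural reading.** In a paragraph about behaviour, main outcomes most likely means the behavioural outcomes. Complete case for outcomes, imputation for covariates and missing = bullying as a sensitivity analysis then fit together. A reader might infer that the plan orders the analyst to impute bullying. The documents do not support that; they support a mismatch of labels that needs correcting.
- **The first sentence need not contradict itself.** It can mean as assigned among responders, or two separate analyses. This stands: the fault is an undefined label.
- **Complete case does not ignore baseline bullying.** It decides who is analysed, not which covariates enter. This stands, and part 3 of the check confirms it: the distortion comes from leaving baseline bullying out of the model. A baseline-adjusted complete-case model would also remove it, so multiple imputation is not the only repair.
- **The dropout patterns are invented.** Nothing in the plan suggests that BullyDown would lose more baseline bullies than control, and the largest shifts are small beside sampling error. This stands.
- **Loss may be smaller than 20%.** The 80% figure is a feasibility threshold. The plan anticipates strong retention, cites 88% and a beta test with no loss, and describes active follow-up. This lowers the size but does not settle the wording.
- **Stakes are limited.** The behavioural outcomes are preliminary, and the feasibility and acceptability criteria do not rest on these sentences. This also stands.

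**Conclusion.** The point holds as a moderate one, worth changing but not a bar to the trial. The intention-to-treat label does not describe a set that leaves out 18 to 30 of 150 youth at 88% to 80% retention. The imputation sentence and the outcome labels in Aim 2 and Table 3 must be reconciled, whichever meaning was intended. The lead estimate as written is unadjusted and complete case, and nothing in the plan guarantees that dropout related to arm and baseline bullying would be corrected.

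The odds ratios of about 0.84 to 1.19 rest on assumed rates and assumed dropout patterns with no true effect. They show that bias is possible in either direction. A reader might infer that the plan will produce a false benefit; the documents do not support that, since they give no dropout pattern by arm and the bias disappears under equal retention or baseline adjustment.

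**What to change.** In section 3E, replace the three sentences with one stated approach:

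- **Lead analysis:** all 150 youth in their assigned arm, by logistic regression adjusted for the baseline value of the outcome. Missing behavioural outcomes are multiply imputed from arm, baseline value, intervention-end value where available, sex and setting.
- **Sensitivity analyses:** the baseline-adjusted complete-case analysis, not labelled intention-to-treat, and missing = bullying. Say whether youth with only one of the two follow-up surveys count as complete cases.
- **Imputation sentence:** list the variables to be imputed, in place of the phrase that excludes the main outcomes, and use the terms of Aim 2 and Table 3 consistently.

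The cost is a short change of wording, made before outcome data are seen, and a little more analysis. No extra data or participants are needed. The downside is reliance on a missing-at-random assumption, which should be stated and which the sensitivity analyses test.
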